5.7 Handling of Missing Data

Missing data will be handled differently depending on the parameter and analysis:

- No imputation for missing values will be applied for PASI and static IGA response variables. The summaries will be based on observed cases only.

- Missing baseline values will not be imputed in any situation.
- Post-baseline values for by-visit data will be summarized and/or analyzed using the Visit Windows from Section 5.6. If a value is not available within a given window, no imputation will be done.
- Missing data for AE relationship will be imputed as “Related.”
- Refer to Appendix 3 for details of imputing partial dates for AE, when applicable.
- Refer to Appendix 4 for details of imputing partial dates for prior and concomitant medication, when applicable.

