4.5 Subject Withdrawals

All subjects have the right to withdraw at any point during the study without prejudice. Lycera must be notified immediately if a randomized subject is withdrawn from the study, and every effort should be made to inform Lycera prior to withdrawing the subject. Subjects who are withdrawn may be replaced at the discretion of Lycera on a case-by-case basis.

Subjects may be withdrawn from the study for the following reasons:

- screen failure: subject does not meet entry criteria and was not randomized
- occurrence of any AE (if the subject withdraws due to an AE the investigator should follow the subject until the AE resolves or stabilizes), concurrent illness, or laboratory abnormality which, in the opinion of the investigator or Lycera, warrants the subject's permanent withdrawal
- subject noncompliance, defined as refusal or inability to adhere to the study schedule or procedures
- at the request of the subject (withdraw consent)
- at the request of the investigator, Lycera, or regulatory authority(ies) for safety, behavioral, or administrative reasons

LYC-30937

Clinical Protocol LYC-30937-2003

Issue Date: 30 August 2016

- subject lost to follow-up (If a subject does not return for a scheduled visit, every effort should be made to contact the subject and/or the subject's family; this effort must be clearly documented)
- other (eg, subject moved)

The subject will be asked to undergo final visit procedures (Visit 6/Week 12) in order to document subject outcome, if possible. The investigator or site staff should inquire about the reason for withdrawal and follow-up with the subject regarding any unresolved AEs.

If a subject withdraws from the study, and withdraws consent for disclosure of future information, no further evaluations should be performed and no additional data should be collected. Lycera may retain and continue to use any data collected before such withdrawal of consent.

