8.0 STATISTICAL AND ANALYTICAL PLAN

8.1 Sample Size Calculation

A total of approximately 30 subjects will be randomized into the study and using a 2:1 randomization ratio of LYC-30937-EC 25 mg or placebo daily.

A sample size of 30 subjects (20 LYC-30937-EC and 10 placebo) will achieve approximately an 80% power to detect difference in the mean percent change from baseline in PASI at Week 12 in the LYC-30937 treatment group compared to the placebo treatment group. The mean percent change from baseline in PASI at Week 12 in the placebo treatment group is assumed to be 16.7% with SD=32.0.^[16] The power was computed assuming the mean percent change from baseline in PASI at Week 12 in the LYC-30937-EC treatment group is at least 52.7% (SD=32.0) for a mean difference of at least 36.0%. The test statistic used is the two-sided t-test. The alpha level of the test was targeted at 0.05.

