4 ANALYSIS SETS

4.1 Full Analysis Set (FAS)

The FAS is defined as all randomized subjects. Subjects will be included in the treatment group to which they were randomized, regardless of the treatment they actually received. All efficacy analyses will be performed on the FAS.

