5.2 Statistical Power and Sample Size Considerations

A total of approximately 30 subjects will be randomized into the study and using a 2:1 randomization ratio of LYC-30937-EC 25 mg or placebo daily.

A sample size of 30 subjects (20 LYC-30937-EC and 10 placebo) will achieve approximately an 80% power to detect difference in the mean percent change from baseline in PASI at Week 12 in the LYC-30937-EC treatment group compared to the placebo treatment group. The mean percent change from baseline in PASI at Week 12 in the placebo treatment group is assumed to be 16.7% with SD=32.0. The power was

computed assuming the mean percent change from baseline in PASI at Week 12 in the LYC-30937-EC treatment group is at least 52.7% (SD=32.0) for a mean difference of at least 36.0%. The test statistic used is the two-sided t-test. The alpha level of the test was targeted at 0.05.

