6 STATISTICAL ANALYSES

6.1 Primary Efficacy Endpoint Analysis

The primary efficacy endpoint is the mean percent change from baseline in PASI score at Week 12. The endpoint will be calculated by taking the Week 12 PASI score and subtracting the baseline PASI score then dividing by the baseline PASI score and multiplying by 100 to get the percentage.

The mean percent change from baseline in PASI scores will be compared between the LYC-30937-EC treatment group and placebo using analysis of covariance with treatment as a factor and baseline as a covariate to assess the null hypothesis that mean percent change from baseline in PASI score at Week 12 in LYC-30937-EC treatment arm equals the mean percent change from baseline in PASI score at Week 12 in the placebo arm.

The mean difference (LYC-30937-EC versus placebo) will also be estimated along with the 95% confidence interval of the difference. If the confidence interval does not contain 0 the null hypothesis will be rejected and the mean percent change from baseline in PASI score at Week 12 will be considered different due to treatment arm.

The observed PASI score at baseline, at Weeks 4, 8, and 12, and the percent change from baseline in PASI score to Week 4, 8, and 12 will be summarized by treatment group using descriptive statistics. The percent change from baseline in PASI score at Week 4 and at Week 8 will be calculated using the same rules as for percent change from baseline at Week 12. In addition, a plot of the mean percent change from baseline in PASI score over visit with one line per treatment (LYC-30937-EC and placebo) will be prepared.

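### The primary ANCOVA leaves out anyone without a PASI on Day 72–92 and ignores their earlier PASI, so unequal response-related loss could shift the 36-point effect by about 2 to 8 points, with no sensitivity analysis planned

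*SAP*

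**What the plan says.** SAP 4.1 defines the full analysis set as everyone randomized and adds: "All efficacy analyses will be performed on the FAS". Protocol 8.2.1 agrees.

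The primary comparison in SAP 6.1 is of percent change in PASI at Week 12, "using analysis of covariance with treatment as a factor and baseline as a covariate". Protocol 8.4 and 8.5.1 name the same model.

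SAP 5.7 rules out imputation for PASI and states: "The summaries will be based on observed cases only". That sentence speaks of summaries. A further item in 5.7 covers by-visit values that are summarized or analyzed, and it leaves an empty window empty. SAP 5.4 computes change only where baseline and post-baseline values both exist.

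SAP 5.6 sets the Week 12 window at Day 72–92 and places an early-termination visit by its study day. One on Day 72–92 is the Week 12 value; one before Day 72 goes to Week 4 or Week 8.

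PASI is scheduled at Weeks 4, 8 and 12/early termination (Protocol Table 1, SAP Appendix 1). For withdrawals, Protocol 4.5 says: "The subject will be asked to undergo final visit procedures (Visit 6/Week 12) in order to document subject outcome, if possible". SAP 6.1 uses Week 4 and Week 8 PASI only for descriptive tables and a plot. Neither document plans a repeated-measures model or a missing-data sensitivity analysis for the primary endpoint.

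**The concern.** The label says all randomized subjects, but the model can use only those with a PASI in one three-week window. The plan thus relies on the missing Week 12 values not distorting the comparison between arms, and it never tests this. PASI at Weeks 4 and 8 bears directly on that question and is already collected.

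Loss related to response is plausible. Protocol 5.6 bars topical and new systemic psoriasis therapy during the study, which gives a subject who is not improving a reason to leave. Protocol 6.4.5 and 6.4.6 lead to withdrawal or permanent discontinuation after more than 3 days off drug. Replacement under Protocol 4.5 is discretionary, and the sample-size section makes no allowance for loss.

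At stake is the single primary test, which has a reject/do-not-reject rule and only 20 and 10 subjects, so a few losses in one arm matter.

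**Working it through.** **1. Planned power.** Inputs from Protocol 8.1 and SAP 5.2: "A sample size of 30 subjects (20 LYC-30937-EC and 10 placebo) will achieve approximately an 80% power to detect difference"; the placebo change "is assumed to be 16.7% with SD=32.0"; the active "treatment group is at least 52.7% (SD=32.0) for a mean difference of at least 36.0" points; "The test statistic used is the two-sided t-test", alpha 0.05. Below, reductions carry a minus sign, as the endpoint formula in SAP 6.1 produces.

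- Standard error = 32.0 × √(1/20 + 1/10) = 12.4.
- Noncentrality = 36.0/12.4 = 2.9, with 28 df.
- Power = 0.8006. The stated 80% reproduces, but only if all 30 subjects have a Week 12 PASI.
- With purely random loss the same formula gives 0.754 at 18/9, 0.700 at 16/8 and 0.648 at 15/7. That is a loss of precision, not bias.

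**2. Who enters the test.** SAP 5.4, 5.6, 5.7 and 6.1 together leave no route into the ANCOVA for a subject without a PASI on Day 72–92.

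**3. Bias under assumed loss.** The documents give no dropout rate, early-visit means or between-visit correlation, so the following are assumptions:

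- Week 12 means −52.7 and −16.7, with Week 4 and Week 8 means at 50% and 80% of these.
- SD 32 at each visit, and between-visit correlation r of 0.5 or 0.8.
- Loss after Week 8 with probability 1/(1 + exp(1.4 − 0.04(x + c))), where x is the Week 8 percent change. For the relative rules c is 0.8 times the size of that arm's Week 12 mean; for the common absolute rule c is 30.

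The true difference is −36.0 except in the last row.

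| Loss rule | Lost, active / placebo | Observed-case difference, r=0.5 | r=0.8 |
|---|---|---|---|
| Random | 25% / 25% | −36.0 | −36.0 |
| Relative to each arm's own mean | about 25% overall | −36.0 | −36.0 |
| Active arm only | 25% / 0% | −40.2 | −42.5 |
| Placebo arm only | 0% / 25% | −31.9 | −29.3 |
| Same absolute rule in both arms | 19% / 36–37% | −33.5 | −31.9 |
| Active arm only, no true effect | 26% / 0% | −4.1 | −6.6 |

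The second row comes from simulated 20/10 trials and the others from 400,000 subjects per arm. For those other rows an estimate was also made by regressing Week 12 on Weeks 4 and 8 among retained subjects in each arm and predicting the lost values. It returned the true difference to within 0.1 each time.

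**4. Effect on the test.** In simulated 20/10 trials (t-test, 8,000 runs) with no true effect and active-arm loss only, type I error was 0.062 (r=0.5) and 0.079 (r=0.8). With no loss it was 0.054 and 0.053.

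**5. Milder loss, other assumptions.** Week 4/8/12 means −25/−42/−52.7 and −8/−13/−16.7, SDs 22/28/32, correlations 0.75/0.60/0.80, with poor responders more likely to leave in both arms:

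- 6% / 15% lost: −33.7, shift 2.3, 2.3/12.8 = 0.18 SE.
- 11% / 24% lost: −32.8, shift 3.2, 3.2/13.5 = 0.24 SE.
- 18% / 36% lost: −31.7, shift 4.3, 4.3/14.4 = 0.30 SE.

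Using Weeks 4 and 8 gave −36.0 each time, with standard errors of 12.8, 13.5 and 14.2. Across all the assumptions tried, with up to about 40% lost in an affected arm, observed cases ranged from −28 to −43. A shift of 8 is 8/14.4 = 0.56 to 8/12.8 = 0.63 of a standard error.

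**The case against.** **Response-related loss need not bias the difference.** A reader might infer that any such loss does. It does not: the arms must be shifted unequally. When loss was symmetric relative to each arm's own mean, observed cases returned −36.0. This stands and limits the claim.

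**Not every early-termination PASI is ignored.** A reader might infer that it is, or that only subjects who complete the study count. SAP 5.6 uses a termination PASI on Day 72–92 as Week 12.

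**The sizes are assumed and modest.** This also stands. At mild loss the shift is about 0.2 of a standard error, and where poor responders leave both arms under a common rule it runs toward no effect. The estimate using Weeks 4 and 8 recovers the truth by construction, because loss was simulated to depend only on observed PASI. The simulations compared unadjusted means with a regression estimate; they fitted neither the baseline-adjusted ANCOVA nor a mixed model at 20 versus 10.

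**A worst-case illustration proves less than it seems to.** If 3 of 20 active subjects with 0% change are lost, the active mean moves from −52.7 to (−52.7 × 20)/17 = −62.0. That is 9.3 points, or 26% of 36. But those subjects are chosen by an unobserved Week 12 value, so a repeated-measures model corrects this only as far as Weeks 4 and 8 predict it.

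**ANCOVA is the protocol's own model,** and this is a 30-subject phase 2a study. Keeping it as primary is defensible. What this does not defend is the absence of any check on the missing values.

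**Conclusion.** The concern holds in a limited form. The primary ANCOVA drops every randomized subject without a PASI on Day 72–92, makes no inferential use of that subject's earlier PASI, and has no missing-data sensitivity analysis beside it. If loss depends on earlier response and moves the arms unequally, the difference is biased by about 2 to 8 points on the planned 36 (roughly 0.2 to 0.6 of a standard error), in either direction. This assumes roughly 6–40% loss in an affected arm. With random or symmetric loss the bias is near zero.

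A reader might go further and infer that the primary result will be biased, or that the trial cannot be interpreted without a new primary model. The documents do not support that: they give no loss rate or mechanism, and the direction is unknown. This is a change that should be made because it is cheap and uses data already collected. It is not a fatal defect.

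**What to change.** Before unblinding, amend SAP 6.1 as follows.

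- Estimate the Week 12 difference and its 95% interval from a repeated-measures model on percent change in PASI at Weeks 4, 8 and 12. Terms: treatment, visit, treatment-by-visit, baseline and baseline-by-visit. Use unstructured covariance with a stated fallback (Toeplitz, then compound symmetry) and Kenward-Roger degrees of freedom.
- Include every randomized subject with a baseline and any post-baseline PASI.
- Keep the observed-case ANCOVA as a sensitivity analysis. At minimum, keep it as primary and pre-specify the repeated-measures model as the sensitivity analysis.
- Add one sensitivity analysis for loss that depends on unobserved response, such as delta-adjusted or placebo-based imputation.
- Use the same approach for %BSA.
- In SAP 5.6, state what happens to a termination PASI that shares a window with a scheduled visit. With visits on Day 57 and Day 65, the closest-to-schedule rule keeps only Day 57, and a repeated-measures model on the same windows would lose the later value too.
- If the primary model changes, record the departure from the protocol's ANCOVA in SAP section 7.

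Cost: SAP text, standard code and a documented departure from the protocol's model, with no new visits or data. The model estimates six covariance parameters from 30 subjects, hence the stated fallback. With complete data the Week 12 contrast is essentially the planned ANCOVA.

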6 STATISTICAL ANALYSES

6.1 Primary Efficacy Endpoint Analysis

The primary efficacy endpoint is the mean percent change from baseline in PASI score at Week 12. The endpoint will be calculated by taking the Week 12 PASI score and subtracting the baseline PASI score then dividing by the baseline PASI score and multiplying by 100 to get the percentage.

The mean percent change from baseline in PASI scores will be compared between the LYC-30937-EC treatment group and placebo using analysis of covariance with treatment as a factor and baseline as a covariate to assess the null hypothesis that mean percent change from baseline in PASI score at Week 12 in LYC-30937-EC treatment arm equals the mean percent change from baseline in PASI score at Week 12 in the placebo arm.

The mean difference (LYC-30937-EC versus placebo) will also be estimated along with the 95% confidence interval of the difference. If the confidence interval does not contain 0 the null hypothesis will be rejected and the mean percent change from baseline in PASI score at Week 12 will be considered different due to treatment arm.

The observed PASI score at baseline, at Weeks 4, 8, and 12, and the percent change from baseline in PASI score to Week 4, 8, and 12 will be summarized by treatment group using descriptive statistics. The percent change from baseline in PASI score at Week 4 and at Week 8 will be calculated using the same rules as for percent change from baseline at Week 12. In addition, a plot of the mean percent change from baseline in PASI score over visit with one line per treatment (LYC-30937-EC and placebo) will be prepared.

6.2 Secondary Efficacy Endpoints Analyses

The following secondary efficacy endpoints will be summarized and compared between the LYC-30937-EC treatment arm and placebo:

- The proportion of subjects who achieve $\geq 75\%$ reduction from baseline in PASI score at Week 12 will be calculated by taking the number of subjects who achieve a percent change from baseline to Week 12 in PASI score of $\geq 75\%$ divided by the total number of subjects in each treatment group. The proportion of subjects in each treatment group will be compared using chi-square test. The difference in proportion of subjects who achieve a $\geq 75\%$ reduction from baseline in PASI score at Week 12 (LYC-30937-EC versus placebo) will also be estimated along with the 95% confidence interval. If the confidence interval does not contain 0 the null hypothesis will be rejected and the proportion of subjects who achieve a $\geq 75\%$ reduction from baseline in PASI score at Week 12 will be considered different due to treatment arm.
- The mean percent change from baseline to Week 12 in the %BSA will be calculated by taking the Week 12 %BSA and subtracting the baseline %BSA then dividing by the baseline %BSA and multiplying by 100 to get the percentage of baseline. The mean percent change from baseline to Week 12 in the %BSA in each treatment group will be compared using the same methodology for the primary efficacy endpoint. The mean difference (LYC-30937-EC versus placebo) will also be estimated along with the 95% confidence interval of the difference. If the confidence interval does not contain 0 the null hypothesis will be rejected and the mean percent change from baseline in %BSA at Week 12 will be considered different due to treatment arm. The observed %BSA at baseline, at Weeks 4, 8, and 12, and the percent change from baseline in %BSA to Week 4, 8, and 12 will be summarized by treatment group using descriptive statistics. The percent change from baseline in %BSA score at Week 4 and at Week 8 will be calculated using the same rules as for percent change from baseline at Week 12. In addition, a plot of the mean percent change from baseline in %BSA over visit with one line per treatment (LYC-30937-EC and placebo) will be prepared.
- The proportion of subjects who achieve “cleared” (score = 0) or “minimal” (score = 1) on the static IGA at Week 12 will be calculated by taking the number of subjects who achieve “cleared” (score = 0) or “minimal” (score = 1) on the static IGA at Week 12 divided by the total number of subjects in each treatment group.

The proportion of subjects in each treatment group will be compared using chi-square test. The difference in proportion of subjects who achieve “cleared” (score = 0) or “minimal” (score = 1) on the static IGA at Week 12 (LYC-30937-EC versus placebo) will also be estimated along with the 95% confidence interval. If the confidence interval does not contain 0 the null hypothesis will be rejected and the proportion of subjects who achieve “cleared” (score = 0) or “minimal” (score = 1) on the static IGA at Week 12 will be considered different due to treatment arm.

- The proportion of subjects who achieve at least a 2 step reduction on the static IGA at Week 12 will be calculated by taking the number of subjects who achieve at least a 2 step reduction on the static IGA at Week 12 (i.e., a score of 5 at baseline to a score of 3 or less at Week 12) divided by the total number of subjects in each treatment group. The results will be summarized and analyzed using the same methodology as for the proportion of subjects who achieve “cleared” (score = 0) or “minimal” (score = 1) on the static IGA at Week 12.

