8.5.2 Secondary Efficacy Endpoint Analyses

The following secondary efficacy endpoints will be summarized and compared between the LYC-30937-EC treatment arm and placebo:

- The proportion of subjects who achieve a $\geq 75\%$ reduction from baseline in PASI at Week 12 will be calculated by taking the number of subjects who achieve a $\geq 75\%$ reduction from baseline in PASI at Week 12 divided by the total number of subjects in each treatment arm. The proportion of subjects in each treatment arm will be compared using a chi-square test.
- The mean percent change from baseline to Week 12 in the BSA will be calculated by taking the Week 12 BSA and subtracting the baseline percent BSA then dividing by the baseline percent BSA and multiplying by 100 to get the percentage of baseline. The mean percent change in each treatment arm will be compared using the same methodology for the primary efficacy endpoint.
- The proportion of subjects who achieve “cleared” (score = 0) or “minimal” (score = 1) on the static IGA at Week 12 will be calculated by taking the number of subjects who achieve “cleared” (score = 0) or “minimal” (score = 1) on the static IGA at Week 12 divided by the total number of subjects in each treatment arm. The proportion of subjects in each treatment arm will be compared using a chi-square test.
- The proportion of subjects who achieve at least a 2 step reduction on the static IGA at Week 12 will be calculated by taking the number of subjects who achieve at least a 2 step reduction on the static IGA at Week 12 (ie, a score of 5 at baseline to a score of 3 or less at Week 12) divided by the total number of subjects in each treatment arm. The proportion of subjects in each treatment are will be compared between treatment arms using a chi-square test.

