5 ANALYSIS PLAN OVERVIEW

5.1 General Methodology

Continuous safety and efficacy endpoints will be summarized using mean, standard deviation, median, minimum, and maximum. Discrete safety and efficacy endpoints will be summarized by the number and percentage of subjects in each category. Continuous efficacy endpoints will be analyzed using an analysis of covariance model with treatment as a factor and baseline value as a covariate. Discrete variables will be analyzed using a chi-square test.

The primary efficacy endpoint will be analysed using a 2-sided significance level $\alpha = 0.05$. All secondary and exploratory efficacy endpoints will also be analysed using 2-sided $\alpha = 0.05$ level of significance. The p-values for the secondary and exploratory endpoints will be considered descriptive and no adjustments will be made for multiplicity.

The analysis of Safety endpoints will be limited to descriptive statistics and by subject listings.

Concentrations of LYC-30937 in plasma and skin tissue will be limited to listings.

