5.4 Change from Baseline

Change from baseline (CFBL) will always be calculated as (post-baseline – baseline). It will be calculated for Subjects with both a baseline and post-baseline value as applicable.

If a baseline value has not been recorded for a parameter, then CFBL will not be calculated for that parameter, and the subject will be excluded from CFBL analysis.

Percent CFBL is the CFBL divided by the baseline value multiplied by 100. Subjects with a value of 0 at baseline or with no baseline value recorded cannot have percent CFBL calculated and they will be excluded from percent CFBL analysis.

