6.3 Exploratory Efficacy Endpoints Analyses

The following exploratory efficacy endpoints will be summarized and compared between the LYC-30937-EC treatment arm and placebo:

- The proportion of subjects who achieve a $\geq 50\%$ reduction from baseline in PASI at Week 12 will be calculated by taking the number of subjects who achieve a percent change from baseline at Week 12 in PASI score $\geq 50\%$ divided by the total number of subjects in each treatment group. The proportion of subjects in each treatment group will be compared using chi-square test. The difference in proportion of subjects who achieve a $\geq 50\%$ reduction from baseline in PASI score at Week 12 (LYC-30937-EC versus placebo) will also be estimated along with the 95% confidence interval. If the confidence interval does not contain 0 the null hypothesis will be rejected and the proportion of subjects who achieve a $\geq 50\%$ reduction from baseline in PASI score at Week 12 will be considered different due to treatment arm.
- The proportion of subjects who achieve a $\geq 25\%$ reduction from baseline in PASI at Week 12 will be calculated by taking the number of subjects who achieve a percent change from baseline at Week 12 in PASI score $\geq 25\%$ divided by the total number of subjects in each treatment group. The proportion of subjects in each treatment group will be compared using chi-square test. The difference in

proportion of subjects who achieve a $\geq 25\%$ reduction from baseline in PASI score at Week 12 (LYC-30937-EC versus placebo) will also be estimated along with the 95% confidence interval. If the confidence interval does not contain 0 the null hypothesis will be rejected and the proportion of subjects who achieve a $\geq 25\%$ reduction from baseline in PASI score at Week 12 will be considered different due to treatment arm.

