7 CHANGES FROM PROTOCOL SPECIFIED ENDPOINTS AND ANALYSES

Primary endpoint definition was updated to be: mean percent change from baseline at Week 12 in PASI.

The following exploratory efficacy endpoints were included:

- The proportion of subjects who achieve a $\geq 50\%$ reduction from baseline in PASI at Week 12.
- The proportion of subjects who achieve a $\geq 25\%$ reduction from baseline in PASI at Week 12.
- Proportion of subjects achieving both a $\geq 75\%$ reduction from baseline in PASI and a static IGA score of 0 (cleared) or 1 (minimal) at Week 12.

Two additional analyses sets were defined: Plasma PK Set and Skin PK Set.
Specific analyses for the exploratory efficacy endpoints were included in Section 6.3.

Adverse events reporting: the SAP does not include any planned summary results for SAEs by system organ class, by severity, and by relationship; and serious adverse events resulting in death will not be listed and summarized separately as noted in the protocol.

APPENDICES

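### The PASI-75, PASI-50 and PASI-25 numerators in SAP 6.2 and 6.3 have the wrong sign: under the SAP's own percent-change formula they count subjects who worsen

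*SAP*

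**What the plan says.** SAP 5.4 fixes the sign of every change score: "Change from baseline (CFBL) will always be calculated as (post-baseline – baseline". It then defines the percentage: "Percent CFBL is the CFBL divided by the baseline value multiplied by 100". SAP 6.1 applies the same formula to the primary endpoint, "taking the Week 12 PASI score and subtracting the baseline PASI score then dividing by the baseline PASI score", times 100. SAP 2.4 gives the PASI range as 0 (no disease) to 72 (maximal disease), so a lower score is better and improvement has a negative percent change.

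SAP 3.6 names the responder endpoints as reductions from baseline of at least 75% (secondary), 50% and 25% (both exploratory). The calculation rules come later. For PASI-75, SAP 6.2 says: "reduction from baseline in PASI score at Week 12 will be calculated by taking the number of subjects who achieve a percent change", and the threshold attached to that percent change is 75% or more, with no minus sign. For PASI-50 and PASI-25, SAP 6.3 says: "reduction from baseline in PASI at Week 12 will be calculated by taking the number of subjects who achieve a percent change", with thresholds of 50% or more and 25% or more, again unsigned.

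Protocol 8.5.2 has no such problem. Its PASI-75 numerator is the number of subjects reaching the stated "reduction from baseline in PASI at Week 12 divided by the total number of subjects in each treatment arm". The protocol has no PASI-50 or PASI-25 endpoint. SAP 7 lists these among its additions ("The following exploratory efficacy endpoints were included"), so SAP 6.3 holds their only calculation rule.

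**The concern.** Each of the three sentences names one quantity (a reduction) and then tells the programmer to count another (a percent change), using a term the SAP has already defined with the opposite sign. The second half of the sentence is the operational rule. Coded as written, it turns the responder definition around: improvement of any size is non-response, and worsening by the threshold amount is response.

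At stake are one secondary and two exploratory endpoints, with their chi-square tests and confidence intervals. The composite endpoint at the end of SAP 6.3 is worded only as a reduction and is sound as it stands, but it would inherit the error if it were built from a PASI-75 flag derived under 6.2. The primary endpoint, %BSA and the two static IGA endpoints do not use these rules.

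**Working it through.** **Inputs.** SAP 5.2 (same figures in Protocol 8.1): 20 active and 10 placebo subjects; mean percent change in PASI 52.7% and 16.7%; SD 32.0; difference 36.0; two-sided t-test at 0.05; power about 80%. SAP 5.4 and 6.1: percent change = 100 × (Week 12 − baseline) / baseline.

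**The plan's own figure.** Noncentrality = 36 / (32 × √(1/20 + 1/10)) = 2.905, df = 28, critical t = 2.048. Power from the noncentral t is 80.06%, so the stated 80% is reproduced. It does not depend on the point raised here.

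**The rule applied to single subjects, baseline PASI 12.**

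| Week 12 PASI | Percent change | PASI-75 as named | PASI-75 numerator as written |
|---|---|---|---|
| 0 | (0 − 12)/12 = −100% | responder | not counted |
| 3 | (3 − 12)/12 = −75% | responder | not counted |
| 21 | (21 − 12)/12 = +75% | non-responder | counted |

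**Expected size.** SAP 5.2 prints 52.7% and 16.7% as positive numbers. They are plainly improvements, so I have signed them by the 5.4/6.1 formula as −52.7 and −16.7. I also assume that percent change is normally distributed, which the documents do not state. With threshold t:

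- intended rule: P(X ≤ −t) = Φ((−t − mean)/32)
- literal rule: P(X ≥ +t) = 1 − Φ((t − mean)/32)
- expected count = probability × 20 (active) or × 10 (placebo)
- chance of no literal responder in either arm = (1 − p_active)^20 × (1 − p_placebo)^10

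For example, PASI-75 on active under the intended rule is Φ((−75 + 52.7)/32) = Φ(−0.697) = 0.243, and 0.243 × 20 = 4.9. Under the literal rule it is 1 − Φ((75 + 52.7)/32) = 1 − Φ(3.991) = 0.000033, and 0.000033 × 20 = 0.0007.

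| Endpoint | Intended, active vs placebo | Literal, active vs placebo | Chance of no literal responder at all |
|---|---|---|---|
| PASI-75 | 4.9 vs 0.3 | 0.0007 vs 0.02 | 0.979 |
| PASI-50 | 10.7 vs 1.5 | 0.01 vs 0.19 | 0.818 |
| PASI-25 | 16.1 vs 4.0 | 0.15 vs 0.96 | 0.312 |

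With no responder in either arm the chi-square statistic cannot be computed.

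**Sensitivity to the SD.** Over an assumed range from SD 40 down to SD 20, the chance of no literal responder is 88% to over 99.9% (PASI-75), 55% to 99.6% (PASI-50) and 12% to 83% (PASI-25).

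**Limit of the model.** A percent change below −100% is impossible, yet the normal model puts Φ((−100 + 52.7)/32) = 7% of the active arm there. Setting those subjects to −100% changes no count, since they are responders under the intended rule and non-responders under the literal one either way.

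**The case against.** The strongest reply is that nobody would be misled. Each bullet in SAP 6.2 and 6.3 calls the endpoint a reduction three times: in its opening words, in the confidence-interval sentence and in the rejection sentence. SAP 3.6 and SAP 7 do so too. A programmer would have to overlook all of this and accept a table in which complete clearance is a failure. The p-values are also only descriptive: "The p-values for the secondary and exploratory endpoints will be considered descriptive and no adjustments will be made for multiplicity". An almost empty responder table beside the mean PASI changes from SAP 6.1 would be noticed. All of that stands, and it limits the weight of the point. PASI-25 is where a miscoded table is least likely to be empty: the chance of at least one false responder is 1 − 0.312 = 69%.

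A second reply is that the SAP itself uses percent change loosely. SAP 5.2 prints improvements as positive, and on that reading the unsigned thresholds return the intended counts. This is a fair description of where the wording may have come from, and it is why the sign reversal in the calculation has to be disclosed. It does not rescue the rule. SAP 5.4 says its sign convention always applies, and SAP 6.1 applies it to this very variable. SAP 5.2 describes planning assumptions and does not derive endpoints.

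A third reply is that the zero-responder probabilities describe an event that would probably be caught. That is so. They show what the rule as written would produce and do not forecast the trial's report.

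**Conclusion.** The point holds. In SAP 6.2 and 6.3 the calculation clauses for PASI-75, PASI-50 and PASI-25 contradict the definitions in SAP 5.4 and 6.1, and as written they select worsening in place of improvement. The contradiction rests on the text alone and needs no assumption. The illustrated counts do: they rest on the planning means with their signs reversed, SD 32 and normality.

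This should be fixed, but it does not threaten the trial's main conclusion. The error came in when the SAP reworded a rule that the protocol states correctly. It was then carried to two endpoints for which the protocol has no rule to fall back on. The primary analysis, sample size and power are unaffected.

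**What to change.** In SAP 6.2, define the PASI-75 numerator as subjects with a percent change from baseline to Week 12 of −75% or lower. In SAP 6.3, use −50% or lower and −25% or lower. Equivalently, add one line to SAP 5.4 defining percent reduction as minus the percent change, and apply the existing thresholds to percent reduction. The PASI part of the composite should refer to the same corrected definition.

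While the SAP is open, it would help to label the 16.7% and 52.7% in SAP 5.2 as reductions, so that the term has one sign throughout. This is tidying only and does not affect the power.

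The cost is three clauses in one document. The responder rule in the protocol needs no change. If the tables have already been programmed, the sign in the code for these three flags should be checked against the corrected text.
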